### **9.2.2 Change in Weight**

[figure not shown]
Weight, change in weight from baseline, and percent change in weight from baseline will be summarized using descriptive statistics at each visit. This information will also be provided graphically for change in weight from baseline and percent change in weight from baseline. In addition, for each patient figures showing change in weight and percent change in weight from baseline over time will be created. Information on the patient's baseline weight, BMI, and BMI z-score will be included in the figure.

[figure not shown]
### **9.2.3 Change in BMI and BMI z-scores**

BMI, change in BMI from baseline, BMI z-score, change in BMI z-score from baseline, and percent change in BMI z-score from baseline will be summarized using descriptive statistics. This information will also be provided graphically for change in BMI from baseline, and change in BMI z-score from baseline. In addition, for each patient figures showing the change in BMI, and the change in BMI z-scores from baseline will be created. Information on the patient's baseline weight, BMI, and BMI z-score will be included in the figure.

### **9.2.4 Ages and Stages Questionnaire, Third Edition**

The normalized categories in the five areas (see Section 3.5.9) and their shift from baseline will be tabulated at each visit. A listing of these data will also be provided.

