**Secondary Endpoints:**

- The following endpoints will be summarized and reported as change from baseline to 52 weeks:
  - Mean absolute change in BMI z-score per age and gender
  - Mean change in percent of the 95th percentile of BMI per age and gender
  - The mean change in vital signs and laboratory evaluations
  - The mean change in bone age
  - Mean change in Ages & Stages Questionnaires, Third Edition (ASQ®-3)
- Frequency and severity of AEs will also be summarized and reported during trial conduct.

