## APPENDICES

### APPENDIX 1. BEALES CRITERIA

BBS clinical diagnosis as per [Beales 1999](#) (with either 4 primary features or 3 primary and 2 secondary features from table below):

Bardet-Biedl Syndrome	
Primary Diagnostic Criteria	
• Rod cone dystrophy	• Learning disabilities
• Polydactyly	• Hypogonadism in males
• Obesity	• Renal anomalies
Secondary Diagnostic Criteria	
• Speech disorder/delay	• Mild spasticity (especially lower limbs)
• Strabismus/cataracts/astigmatism	• Diabetes mellitus
• Brachydactyly/syndactyly	• Dental crowding/hypodontia/small roots/high arched palate
• Developmental delay	• Left ventricular hypertrophy/congenital heart disease
• Polyuria/polydipsia (nephrogenic diabetes insipidus)	• Hepatic fibrosis
• Ataxia/poor coordination	

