### **3.5.9 Ages & Stages Questionnaires®, Third Edition (ASQ®-3)**

The ASQ®-3 is a developmental screening tool that assesses developmental progress in children between one month to 5 ½ years. The ASQ®-3 is intended for use at six-month intervals between 6 months and 3 years of age, and then at one-year intervals through age 5. Thus, for patients who enter the study at ages between 2 years and 3 years, the ASQ-3 will be administered at the Enrollment (Baseline) Visit, Week 28 visit and EOT Visit. For patients who enter the study between the ages of 3 and 6 years old, the ASQ-3 will only be administered at the Enrollment (Baseline) Visit and EOT Visit.

The ASQ-3 consists of five areas: communication, gross motor, fine motor, problem solving, and personal-social. Each area consists of six questions that are scored Yes = 10 points, Sometimes = 5 points, and Not yet = 0 points. The 10 free-response items will not be analyzed.

[figure not shown]
[figure not shown]
[figure not shown]
The total area score is calculated by first adding up the questions within each area and then comparing the total area score to the respective cutoff score on the ASQ-3 scoring sheet to be normalized to one of three categories, which indicate whether the child's development appears to be on schedule.

[figure not shown]
- Below the cut-off = Further assessment with a professional may be needed.
- Close to the cut-off = Providing learning activities and monitor.

[figure not shown]
- Above the cut-off = The child's development appears to be on schedule.

The following table presents ASQ-3 Referral cutoff scores and monitoring zone cutoff scores used in the analysis:

PARCAT2	PARAM	Referral Cutoff	Monitoring zone Cutoff
30 Month Questionnaire	Communication - 30	33.30	43.56
36 Month Questionnaire	Communication - 36	30.99	41.43
42 Month Questionnaire	Communication - 42	27.06	38.54
48 Month Questionnaire	Communication - 48	30.72	41.82
54 Month Questionnaire	Communication - 54	31.85	42.82
60 Month Questionnaire	Communication - 60	33.19	42.80
30 Month Questionnaire	Gross Motor - 30	36.14	44.84
36 Month Questionnaire	Gross Motor - 36	36.99	45.84
42 Month Questionnaire	Gross Motor - 42	36.27	45.15
48 Month Questionnaire	Gross Motor - 48	32.78	42.74
54 Month Questionnaire	Gross Motor - 54	35.18	44.58
60 Month Questionnaire	Gross Motor - 60	31.28	41.72
30 Month Questionnaire	Fine Motor - 30	19.25	33.02
36 Month Questionnaire	Fine Motor - 36	18.07	32.57

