42 Month Questionnaire	Fine Motor - 42	19.82	33.68
48 Month Questionnaire	Fine Motor - 48	15.81	30.58
54 Month Questionnaire	Fine Motor - 54	17.32	31.72
60 Month Questionnaire	Fine Motor - 60	26.54	39.05
30 Month Questionnaire	Problem Solving - 30	27.08	38.63
36 Month Questionnaire	Problem Solving - 36	30.29	41.13
42 Month Questionnaire	Problem Solving - 42	28.11	39.82
48 Month Questionnaire	Problem Solving - 48	31.3	42.04
54 Month Questionnaire	Problem Solving - 54	28.12	39.68
60 Month Questionnaire	Problem Solving - 60	29.99	41.29
30 Month Questionnaire	Personal - Social - 30	32.01	41.94
36 Month Questionnaire	Personal - Social - 36	35.33	44.07
42 Month Questionnaire	Personal - Social - 42	31.12	41.25
48 Month Questionnaire	Personal - Social - 48	26.6	38.47
54 Month Questionnaire	Personal - Social - 54	32.33	42.55
60 Month Questionnaire	Personal - Social - 60	39.07	46.96

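### The SAP summarises the ASQ-3 only as a three-category shift, so the protocol's mean-change endpoint is not produced and further decline within the lowest category does not show in the summary

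*SAP*

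**What the plan says.** The protocol synopsis and Table 2 list "Mean change in Ages & Stages Questionnaires, Third Edition" among the secondary endpoints to be reported as change from baseline to 52 weeks.

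SAP 3.5.9 describes the scoring of the five areas: "Each area consists of six questions that are scored Yes = 10 points, Sometimes = 5 points, and Not yet = 0 points". The area total is then reduced by "comparing the total area score to the respective cutoff score on the ASQ-3 scoring sheet to be normalized to one of three categories". The lowest of the three is defined as "Below the cut-off = Further assessment with a professional may be needed". The section prints a referral and a monitoring cut-off for each area on six age forms, from 30 to 60 months; the last row is "Personal - Social - 60".

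SAP 9.2.4 sets the analysis: "The normalized categories in the five areas (see Section 3.5.9) and their shift from baseline will be tabulated at each visit". It adds: "A listing of these data will also be provided". It names no descriptive statistics for the area score or its change. The table in SAP 16.2 for changes from the protocol's planned analyses shows headings and no entries.

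**The concern.** There are two linked problems.

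First, a stated secondary endpoint has no matching output. The SAP does plan descriptive summaries of change for the other change-from-baseline secondary endpoints: percent of the 95th BMI percentile (9.2.1), BMI z-score (9.2.3), laboratory values (10.4), vital signs (10.5) and bone age (10.8). The ASQ-3 is the exception, and the difference is not declared.

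Second, the substituted summary has a floor in each area. A child already below the referral cut-off can only stay or move up in that area's table, however far the score falls. This matters because about 5 or more of the 10-15 planned children have Bardet-Biedl syndrome (BBS). The Beales criteria in protocol Appendix 1 include "Learning disabilities" as a primary feature, with developmental delay, speech disorder or delay, and poor coordination as secondary ones. Low baseline scores in some areas are therefore plausible. The ASQ-3 is also the only scored developmental measure visible in the public documents, for children aged 2 to under 6 who are treated for a year.

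**Working it through.** The plan gives no sample size, power or precision figure for this endpoint, so there is nothing to reproduce. The check is an enumeration.

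**Inputs (all from SAP 3.5.9).** Six items scored 0, 5 or 10 give area totals of 0 to 60 in steps of 5, which is 13 attainable levels. There are 30 pairs of referral and monitoring cut-offs (five areas, six forms). I assume that a child's baseline and Week 52 forms are 12 months apart: 30 to 42, 36 to 48, 42 to 54 or 48 to 60 months. That gives 5 × 4 = 20 area-by-form transitions.

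**Step 1: width of the lowest category.** It holds between 4 of the 13 levels (for example Fine Motor at 48 months, cut-off 15.81, scores 0-15) and 8 of the 13 (for example Gross Motor at 36 months, cut-off 36.99, scores 0-35). On a fixed form, a fall of up to 15 to 35 points therefore stays in one cell.

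**Step 2: possible declines from the lowest category.** With k levels below the cut-off on the baseline form, there are k(k − 1)/2 pairs in which the later score is lower (k = 4, 6, 7, 8 gives 6, 15, 21, 28).

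| Area | 30→42 | 36→48 | 42→54 | 48→60 | Sum |
|---|---|---|---|---|---|
| Communication | 21 | 21 | 15 | 21 | 78 |
| Gross Motor | 28 | 28 | 28 | 21 | 105 |
| Fine Motor | 6 | 6 | 6 | 6 | 24 |
| Problem Solving | 15 | 21 | 15 | 21 | 72 |
| Personal-Social | 21 | 28 | 21 | 15 | 85 |
| Total | | | | | 364 |

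**Step 3: what the shift table shows.** None of the 364 appears as worsening; this follows by construction, since no lower category exists. One appears as improvement: Personal-Social 35 on the 36-month form (below 35.33) falling to 30 on the 48-month form (between 26.60 and 38.47). A change in area score would be negative for all 364. These are counts of possible score pairs, not probabilities.

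**Step 4: a hypothetical child.** Communication 25 on the 42-month form is 25 − 27.06 = −2.06 from referral. A score of 5 on the 54-month form is 5 − 31.85 = −26.85. A 20-point loss on a 0-60 scale is tabulated as no shift.

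**Step 5: limits of a raw change.** Over 12 months the referral cut-off moves by between 26.60 − 35.33 = −8.73 (Personal-Social, 36 to 48) and 39.07 − 26.60 = +12.47 (Personal-Social, 48 to 60). The median absolute move over the 20 transitions is (1.31 + 1.50)/2 ≈ 1.4 points. In 16 of 20 it is under 5 points, one scoring step. The four exceptions are 6.24 (Communication, 30 to 42), 8.73, 10.73 (Fine Motor, 48 to 60) and 12.47. At the extreme, an unchanged Personal-Social score of 35 goes from 35 − 26.60 = +8.40 at 48 months to 35 − 39.07 = −4.07 at 60 months, with a raw change of 0.

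**The case against.** The best defence is that the ASQ-3 is a screening tool whose age-specific cut-offs exist because forms differ. Categories judged against the child's own form are then a defensible summary, and a raw change across forms is not on one fixed scale. This stands as a reason to keep the shift table and to footnote the score change. It does not explain why a stated endpoint is dropped without a declaration, and for most transitions the drift is under one scoring step.

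A reader might infer that the trial cannot detect developmental decline in children with BBS. The documents do not support that:

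- A per-patient listing is planned. SAP Section 4 allows derived variables to be listed as appropriate, so area scores may appear, although 9.2.4 does not name them. With 10-15 children a listing will be read closely.
- The floor applies per area, and to any child in the lowest category whatever the diagnosis. A child at the floor in one area can still show worsening in others.
- Beales criteria can be met with no developmental feature, for example by rod cone dystrophy, polydactyly, obesity and renal anomalies. No baseline ASQ-3 distribution is given.
- The abbreviated physical examination includes a neurologic examination (protocol 8.1.4), and a pre-existing condition that deteriorates is recorded as an adverse event (protocol 8.6.5). These are not scored developmental measures, but they are another route.

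Nor is the table as a whole one-sided. It has a ceiling too: a child above the monitoring cut-off can only stay or worsen.

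A reader might also want to replace the raw score with a scaled one, such as (score − referral cut-off)/(monitoring − referral cut-off). That has its own artefact. A constant Personal-Social score of 0 gives −26.60/11.87 = −2.24 at 48 months and −39.07/7.89 = −4.95 at 60 months, an apparent decline with no score change. One such child could dominate a mean over about five.

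Finally, the empty table in SAP 16.2 may reflect text lost in reading the PDF, so it is weak evidence. The gap between the protocol endpoint and SAP 9.2.4 does not depend on it.

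**Conclusion.** The point holds for the planned summary reporting. As written, SAP 9.2.4 does not produce the protocol's mean change in ASQ-3, and SAP 16.2 as shown does not declare the difference. In any area where a child starts below the referral cut-off, the shift table hides further decline: 0 of 364 enumerated declines show as worsening and 1 shows as improvement.

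The practical size is unknown. It depends on how many children start below a cut-off and in which areas; among the BBS children that could be none or all. The count also assumes forms 12 months apart. The claim does not extend to the listings or to adverse event reporting. This is a descriptive secondary endpoint in a trial without hypothesis testing, so the point is worth correcting but does not bear on the primary results.

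**What to change.** - **SAP 9.2.4, summary.** Keep the shift table. Add, for each area, the total score (0-60) and its change from baseline to Week 52, with n, mean, SD, median, minimum and maximum.
- **SAP 9.2.4, listing.** State that the listing shows, for each child and visit, the area score, the age form used and the points above or below that form's referral cut-off. SAP 3.5.9 prints no cut-offs below the 30-month form although entry is from age 2, so add any others that are used.
- **Footnote.** Say that baseline and Week 52 scores usually come from different age forms, whose referral cut-offs move by −8.73 to +12.47 points over 12 months (under 5 points in 16 of 20 area-by-form transitions).
- **SAP 16.2.** Record any departure from the protocol endpoint that remains.

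A scaled score is optional and should not replace the change in area score.

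The cost is SAP wording and one more summary per area, from data already collected. The downside is a mean change with limited comparability across forms, which the footnote and listing make visible.

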## **10 Safety Analysis**

### **10.1 Safety Endpoints**

All safety endpoints will be based on the Safety Population. Safety endpoints include:

- Safety and tolerability assessed by the frequency and severity of AEs (see [Section 10.3](#) for more details)
- Safety and tolerability assessed by vital signs (see [Section 10.5](#) for more details)
- Safety and tolerability assessed by laboratory evaluations (see [Section 10.4](#) for more details)
- Change from baseline in metabolic parameters following treatment with setmelanotide, including fasting glucose, HbA1c, lipid profiles (total-, high-density lipoprotein [HDL]-, and low-density lipoprotein [LDL]-cholesterol, triglycerides).

### **10.2 Study Treatment**

#### **10.2.1 Study Drug Exposure**

Dosing of study treatment will be monitored throughout the study by having the patient complete a daily dosing log that records daily dosing information, including:

- The time of dosing

- If the injection occurred (Yes/No)
- Reason for not injecting (Forgot, Trouble with injection, Ran out/misplaced drug, Other)

Study treatment duration, in weeks, will be calculated as the number of weeks patients were administered study drug and will be summarized using descriptive statistics. Study treatment duration will be calculated using the following formula:

$$\textit{Treatment Duration (weeks)} = \frac{(\textit{Date of last injection} - \textit{Date of first injection}) + 1}{7}$$

For each patient, total exposure (mg) will be summarized descriptively in a table as the total sum of all dose mg that a patient receives throughout the study.

For each patient, study drug compliance will be calculated using the following formula:

$$\textit{Compliance (\%)} = \left( \frac{\textit{Number of daily dosing logs where injection occurred}}{\textit{Date of last injection} - \textit{Date of first injection} + 1} \right) \times 100\%$$

Patient compliance with study drug will be summarized descriptively in a table. The number of patients who experienced at least one dose interruption will also be presented, as well as the reason for the interruption.

Study drug compliance will be presented by patient in a data listing. The listing will show the daily dosing study day, date of the daily dosing log, indicator if patient was injected, reason for not injecting, treatment duration, and compliance percentage.

### **10.2.2 Treatment Administration**

Study treatment administration will be presented by patient in a data listing. The listing will show the date study drug was dispensed, items dispensed, treatment administration date, indicator if patient was injected, reason for not injecting, dose (mg), injection location, and kit number. A listing containing the patient supply accountability log will also be created. This listing will contain the article name, item number, expiry date, lot ID, item type, unit, quantity dispensed, item status, date returned/reported, item condition, quantity returned, amount returned, and any comments.

### **10.2.3 Injection Site Evaluation**

Injection site evaluation (described in [Section 3.5.6](#)) at each visit will be summarized using descriptive statistics.

Injection site evaluation will be presented by patient in a data listing. The listing will show the date of evaluation, indicator if patient was evaluated, reason evaluation was not performed, reaction, finding, indicator if CS, length (mm), and width (mm).

### **10.2.4 Dose Level Changes**

Any dose level changes that occur throughout the study will be captured in a data listing. For each patient, the visit, reason for dose level change, date of new dose, new dose level (mg), and planned location for injection will be presented.

### **10.3 Adverse Events**

An AE is any untoward medical occurrence in a patient or clinical study patient, temporally associated with the use of study treatment, whether or not considered related to the study treatment. An AE can therefore be any unfavorable and unintended sign (including an abnormal laboratory finding), symptom, or disease (new or exacerbated) temporally associated with the use of study treatment. AEs, including Serious Adverse Events (SAE), will be collected from the provision of informed consent until the EOS visit. All AEs reported will be coded using the MedDRA version in force at the time of database freeze) and classified by MedDRA SOC and PT. The MedDRA version used for the coding will be noted as a footnote in the tables and listings.

All AEs will be presented by patient in a data listing. The listing will show the verbatim term, MedDRA SOC, MedDRA PT, event start date, event end date (or ongoing), SAE indicator, severity, relationship to study drug, action taken with study drug, action taken, and outcome.

#### **10.3.1 Overview of Adverse Events**

An overview summary table of AEs will be provided, including the number and percentage of patients reporting an AE for the following categories:

- Patients with at least one treatment-emergent AE (TEAE)
- Patients with at least one TEAE related to study drug
- Patients with at least one TEAE leading to drug discontinuation
- Patients with at least one TEAE leading to study discontinuation
- Patients with at least one serious TEAE
- Patients with at least one serious TEAE related to study drug
- Patients with AE resulting in death on study

#### **10.3.2 Treatment-Emergent Adverse Events**

A TEAE is any AE that begins or worsens in intensity on or after the date of the first administration of study drug. Summaries of TEAEs (including number and percentage of patients) will be displayed by the following:

- TEAEs by MedDRA SOC and PT
- TEAEs related to study drug by MedDRA SOC and PT

- TEAEs leading to drug discontinuation by MedDRA SOC and PT
- TEAEs leading to study discontinuation by MedDRA SOC and PT
- Serious TEAEs by MedDRA SOC and PT
- Serious TEAEs related to study drug by MedDRA SOC and PT
- AEs resulting in death on study by MedDRA SOC and PT

The number and percentage of patients who experienced at least one of the events listed above will be summarized overall and for each SOC and each PT. SOC and PTs will be presented in descending frequency first and then alphabetically if there are ties. Each patient will contribute at most one count per summarization category. In other words, if a patient has more than one TEAE with same PT, the patient will be counted only once for that PT. Similarly, if a patient has more than one TEAE for a SOC, the patient will be counted only once in that SOC and PT.

### **10.3.3 Severity of the Adverse Event**

TEAEs will also be summarized by maximum severity and will follow the same methods specified in [Section 10.3.2](#). The severity of the TEAE is classified into the five Common Terminology Criteria for Adverse Events (CTCAE) categories of Mild, Moderate, Severe, Life Threatening or Disabling, and Death. If a patient has multiple occurrences of the same MedDRA SOC or PT, then only the most severe event will be summarized in the tables for that SOC and PT. If the severity assessment is missing, the severity of 'Severe' will be assumed.

### **10.3.4 Relationship to Study Drug**

TEAEs will also be summarized by relationship to study drug and will follow the same methods specified in [Section 10.3.2](#). The relationship of the TEAE is classified into two categories of Related and Not Related. If the relationship assessment is missing, the relationship will be considered related. Related TEAEs will also be summarized by MedDRA SOC, PT and maximum severity (defined in [Section 10.3.3](#)). If the patient experiences both a related and not related TEAE within a particular SOC or PT, only the related TEAE will be summarized in the table.

### **10.3.5 Death, Serious Adverse Events, Adverse Events Leading to Discontinuation**

Serious TEAEs, TEAEs leading to death, and TEAEs leading to study drug discontinuation will be summarized, in separate summary tables, by MedDRA SOC and PT, following the same methods specified in [Section 10.3.2](#). Furthermore, serious TEAEs will also be summarized, separately, by MedDRA SOC, PT, maximum severity/relationship/ relationship and maximum severity (defined in [Section 10.3.3](#) and [10.3.4](#)).

Additionally, separate patient listings also will be provided for the following: patient deaths, SAEs, and AEs leading to study discontinuation and drug discontinuation.

The patient death listing will include any AEs that lead to an outcome of death, and will show the verbatim term, MedDRA SOC, MedDRA PT, event start date, date of death, severity, relationship to study drug, action taken with study drug, action taken, and outcome.

[figure not shown]
The SAE listing will include any AEs that are classified as an SAE, and will show the verbatim term, MedDRA SOC, MedDRA PT, event start date, event end date (or ongoing), SAE category, severity, relationship to study drug, action taken with study drug, action taken, and outcome.

The AEs leading to discontinuation listing in will include any AEs that lead to an outcome of discontinuation or study drug withdrawn, and will show the verbatim term, MedDRA SOC, MedDRA PT, event start date, event end date (or ongoing), SAE indicator, severity, relationship to study drug, and outcome.

